#### 6.3.1.2. Disease Activity Score for 28 Joint Count using CRP

The DAS28(CRP) score is calculated as follows:

$$\text{DAS28(CRP)} = 0.56\sqrt{\text{TJC28}} + 0.28\sqrt{\text{SJC28}} + 0.36 \ln(\text{CRP} + 1) + 0.014 \times \text{SGA} + 0.96,$$

where

CRP = hsCRP measurement (mg/L)

SGA = subject's global assessment of disease activity on a 0-100mm VAS

Higher DAS28(CRP) value indicates more severe disease activity.

No component-level imputation will be performed for the calculation of DAS28(CRP) for the primary analyses. If any components are missing, the DAS28(CRP) will be set as missing.

### 6.3.1.3. 36-Item Short-form Health Survey

The SF-36 Version 2 is a 36-item, self-reported, generic, comprehensive, and health-related quality of life questionnaire that yields an 8 health domains (physical functioning, role-physical, bodily pain, general health, vitality, social functioning, role-emotional, and mental health). Each domain is scored by summing the individual items and transforming the scores into a 0 to 100 scale with higher scores indicating better health status or functioning. In addition, 2 summary scores, the physical component score (PCS) and the mental component score (MCS) will be evaluated based on the 8 SF-36 domains.

### 6.3.1.4. FACIT-Fatigue

The FACIT-Fatigue scale is a brief, 13-item, symptom-specific questionnaire that specifically assesses the self-reported severity of fatigue and its impact upon daily activities and functioning in the past 7 days. The FACIT-Fatigue uses 0 (“not at all”) to 4 (“very much”) numeric rating scales. Negatively stated items are reversed by subtracting the response from “4” before being added to obtain a total score.

## 6.3.2. Analysis Methods for Key Secondary Efficacy Endpoints

Hypothesis testing on the key secondary efficacy endpoints will commence after the testing on the primary efficacy endpoint reaches statistical significance, and will be performed according to the hierarchical testing principle at the 2-sided 0.05 level as described in Section 3.5. If a null hypothesis is not rejected, formal sequential testing will be stopped and only nominal significance will be reported for the remaining hypotheses.

For proportion of subjects who achieve  $\text{DAS28(CRP)} < 2.6$  at Week 24, the similar logistic regression analysis with the same model specification as the primary endpoint analysis described in Section 6.2.3 will be adopted for the comparisons between treatment groups. The NRI method will be used to impute missing values. Comparisons will be made between each filgotinib dose group and the MTX alone group. The p-value from the logistic regression model will be reported for statistical inference. The 2-sided 95% CI of the response rate of  $\text{DAS28(CRP)} < 2.6$  at Week 24 based on normal approximation will be provided for each treatment group. In addition, non-stratified response rate difference between treatment groups with its 95% CI based on the normal approximation will be provided.

The change from Baseline in HAQ-DI at Week 24 will be analyzed using the mixed-effects model for repeated measures (MMRM) that include all available data at postbaseline visits. Subjects that have a baseline value and at least one postbaseline value are included in the analysis. The MMRM model will be used to evaluate treatment effect on change score from Baseline, with baseline value, stratification factors, treatment, visit, and treatment by visit interaction included as fixed effects and subject being the random effect. An unstructured variance-covariance matrix will be used. The Kenward-Roger method will be used to estimate the degrees of freedom. Missing change scores due to missing study visits or early withdrawal will not be otherwise imputed using the MMRM approach. The least squares (LS) means along

with the two-sided 95% CIs and the p-value for the difference in mean change from Baseline in HAQ-DI at Week 24 between each filgotinib dose group and MTX alone group from MMRM will be provided.

The change from Baseline in SF-36 PCS, FACIT-Fatigue, and mTSS at Week 24 will be analyzed using similar MMRM method as HAQ-DI, by including all available data at postbaseline visits. To test for a treatment difference between each filgotinib dose group and MTX alone group, LS mean difference along with 95% CI and p-values from the MMRM model will be presented.

The proportions of subjects achieving DAS28(CRP) < 2.6 (using NRI) will be plotted over time by treatment. Plots of mean  $\pm$  SD of changes from Baseline in HAQ-DI, SF-36 PCS, FACIT-Fatigue scale score, and mTSS over time will be presented, respectively.

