#### **6.3.3.2. Missing Data Imputation Analyses**

The following imputation methods will be explored:

- Change from Baseline in the HAQ-DI score at Week 24
  - 1) MI: All subjects with baseline measurement will be included. The MI procedure replaces each missing value with a set of plausible values that represent the uncertainty about the right value to impute. Multiple imputed datasets will be generated based on linear regression models on observed HAQ-DI scores. These multiple imputed data sets are then analyzed by using the analysis method specified in Section 6.3.2 for complete data. The result of each set of imputed data will be combined using Rubin's rule {Rubin 1987} and provided. Stratification factors and baseline values will be included in the imputation model as covariates, and all available data at baseline and postbaseline visits up to the time point of interest will be included in the longitudinal model.
  - 2) Tipping point analysis: All subjects with baseline measurement will be included. To assess the robustness of analysis results for HAQ-DI change from Baseline at Week 24 under MNAR assumption, a set of shift parameter that adjust the imputed values for observation will be examined {Yuan 2014}. The shift parameter that alters the conclusion of the hypothesis testing for HAQ-DI change from Baseline at Week 24 under the MAR assumption will be reported as the tipping point and provided. The tipping point analysis will be conducted by iteratively assigning plausible outcomes to missing values for subjects in different treatment groups independently until the analyses conclusion is reversed. The same analysis method as specified in Section 6.3.2 will be applied when analyzing adjusted data generated under each plausible shift parameter.

- Change from Baseline in mTSS at Week 24
  - 1) MI: Similar MI procedure used for analyzing the change from Baseline in the HAQ-DI score at Week 24 will be performed for change from Baseline in the mTSS at Week 24.
  - 2) Tipping point analysis: Similar tipping point analysis method used for analyzing the change from Baseline in the HAQ-DI score at Week 24 will be performed.
- Proportion of subjects who achieve DAS28(CRP) < 2.6 at Week 24
  - 1) The analysis using the same logistic regression model specified in Section 6.3.2 will be performed by using OC and LOCF methods as described in Section 6.1.

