  - 2) MI: All subjects with baseline measurement will be included. The MI procedure replaces each missing composite DAS28(CRP) value with a set of plausible values that represent the uncertainty about the right value to impute. Baseline value and stratification factors will be included in the imputation model as covariates, and all available data at baseline and all post-baseline visits through the last available visits will be included in the longitudinal model. The multiple imputed datasets will be generated. These multiple imputed data sets are then used to identify subjects with  $\text{DAS28(CRP)} \leq 3.2$  at Week 12, and analyzed by using the analysis method specified in Section 6.3.2 for complete data. The results from each set of imputed data sets will then be combined using Rubin's rule {Rubin 1987}.
  - 3) Tipping point analysis: Similar tipping point method as described in Section 6.2.4.2 will be applied to DAS28(CRP) < 2.6 response rate at Week 24.
- Change from Baseline in SF-36 PCS at Week 24
  - 1) MI: Similar MI procedure used for analyzing the change from Baseline in the HAQ-DI score at Week 24 will be performed.
  - 2) Tipping point analysis: Similar tipping point analysis method used for analyzing the change from Baseline in the HAQ-DI score at Week 24 will be performed.
- Change from Baseline in FACIT-Fatigue at Week 24
  - 1) MI: Similar MI procedure used for analyzing the change from Baseline in the HAQ-DI score at Week 24 will be performed.
  - 2) Tipping point analysis: Similar tipping point analysis method used for analyzing the change from Baseline in the HAQ-DI score at Week 24 will be performed.

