#### **6.4.2. Analysis Methods for Other Secondary Efficacy Endpoints**

The FAS will be used for all summaries and analyses of other secondary efficacy endpoints. Nominal p-values will be presented, if applicable.

The proportion of subjects who achieve ACR20/50/70 and proportion of subjects with change in HAQ-DI  $\geq 0.22$  (ie, reduction in HAQ-DI  $\geq 0.22$ ), DAS28(CRP)  $\leq 3.2$ , and DAS28(CRP)  $< 2.6$  will be analyzed using the the same logistic regression method with NRI as the primary endpoint analysis described in Section 6.2.3. The 2-sided 95% CIs for the proportion based on normal approximation will be provided for each treatment group. The OC and LOCF values will be analyzed as a sensitivity approach to the primary method that uses NRI.

The proportion of subjects having no radiographic progression at Week 24 and 52 will be analyzed using the same logistic regression method based on the OC. Comparison will be made between each filgotinib dose group and MTX alone group. The 2-sided 95% CIs for the proportion based on normal approximation will be provided for each treatment group. In addition, similar analysis will be performed with thresholds of 0 and the smallest detectable change (SDC). The change from Baseline in mTSS, DAS28(CRP), CDAI and SDAI will be analyzed using MMRM method that include all available data at postbaseline visits through Week 52. The MMRM models will include baseline value, stratification factors, treatment, visit, and treatment by visit interaction included as fixed effects and subject being the random effect. An unstructured variance-covariance matrix will be used. The Kenward-Roger method will be used to estimate the degrees of freedom. Missing change scores due to missing study visits or early withdrawal will not be otherwise imputed using the MMRM approach. The LS means along with 95% CIs of the difference in mean change scores from Baseline between each filgotinib dose group and MTX alone group from the MMRM model will be provided for each postbaseline visit. Descriptive statistics of actual and change in DAS28(CRP), CDAI, SDAI, and mTSS from baseline to postbaseline visits will also be performed by treatment and visit.

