## Appendix 6. SAS Programming for Tipping Point Analysis for Binary Endpoint

The following **%tp\_binary** macro generates multiple imputed data and a set of the shift parameters that adjust the imputed values will be examined.

```

/*-----*/
/*--- Delta-Adjustment Method for Tipping Point Analysis for Binary Endpoint ---*/
/*---
/*--- Generate imputed data set for specified shift parameters ---*/
/*--- data= input data set ---*/
/*--- smin= min shift parameter for active drug ---*/
/*--- smax= max shift parameter for active drug ---*/
/*--- sinc= increment of the shift parameter for active drug ---*/
/*--- pmin= min shift parameter for placebo drug ---*/
/*--- pmax= max shift parameter for placebo drug ---*/
/*--- pinc= increment of the shift parameter for placebo drug ---*/
/*--- trt= treatment group indicator ---*/
/*--- out= output imputed data set ---*/
/*-----*/

%macro tp_binary( data=, smin=, smax=, sinc=, pmin=, pmax=, pinc=, trt=, out=);
  data &out;
  set _null_ ;
  run;

  %let ncase_pbo = %sysevalf( (&pmax-&pmin)/&pinc, ceil );

  %do pc=0 %to &ncase_pbo;

    %let pj= %sysevalf( &pmin + &pc * &pinc);

    /*----- # of shift values -----*/
    %let ncase= %sysevalf( (&smax-&smin)/&sinc, ceil );

    /*----- Imputed data for each shift -----*/
    %do jc=0 %to &ncase;

      %let sj= %sysevalf( &smin + &jc * &sinc);

      proc mi data=&data seed=14823 nimpute=20 out=outmi;
        var trt01pn strat1V strat2V strat3V das28n;
        class trt01pn strat1V strat2V strat3V das28n;
        monotone logistic (das28n / link=glogit);
        mnar adjust( das28n(event='1') / adjustobs=(trt01pn="&trt") shift= &sj)
          adjust( das28n(event='1') / adjustobs=(trt01pn='3') shift= &pj);

      run;

      data outmi;
        set outmi;
        Shift Trt= &sj;
        Shift_Pbo= &pj;

      run;

```

```
data &out;  
    set &out outmi;  
run;  
%end;  
%end;  
%mend tp_binary;
```

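### DAS28(CRP)<2.6 is the only key secondary endpoint tested without its baseline value: the test is valid, but a cheap possible gain in precision is left unused

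*SAP*

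**What the plan says.** SAP 6.3 names five key secondary endpoints; DAS28(CRP)<2.6 is the only binary one. For it, SAP 6.3.2 states that "the similar logistic regression analysis with the same model specification as the primary endpoint analysis described in Section 6.2.3 will be adopted". Section 6.2.3 defines that model as treatment groups plus stratification factors, with non-responder imputation (NRI). The p-value comes from the model. The only between-group estimate lies outside it: a "non-stratified response rate difference between treatment groups with its 95% CI based on the normal approximation will be provided".

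The HAQ-DI model is fitted "with baseline value, stratification factors, treatment, visit, and treatment by visit interaction included as fixed effects". For three others, "The change from Baseline in SF-36 PCS, FACIT-Fatigue, and mTSS at Week 24 will be analyzed using similar MMRM method as HAQ-DI", so they carry baseline too.

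Baseline DAS28(CRP) is already derived (SAP 5.2). It also enters this endpoint's multiple-imputation (MI) sensitivity analysis in 6.3.3.2: "Baseline value and stratification factors will be included in the imputation model as covariates". The Appendix 6 tipping-point code does not use it; its variable list is "var trt01pn strat1V strat2V strat3V das28n". For DAS28(CRP)≤3.2, and for <2.6 at other visits, SAP 6.4.2 uses the "same logistic regression method with NRI as the primary endpoint analysis described in Section 6.2.3".

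Protocol 8.5.2 adjusted the binary endpoints for stratification factors only, by CMH. SAP 6.5 replaces CMH with logistic regression on the same factors because some strata are sparse.

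**The concern.** ACR20 is defined by percentage improvement from baseline. DAS28(CRP)<2.6 is a fixed threshold, so a subject's starting score may well affect the chance of crossing it. A prognostic covariate left out of a logistic model costs precision.

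Hypotheses 8 to 10 are formal tests, and hypotheses 11 to 17 are reached only if all three reject. Any lost power therefore passes down the list, though only in trials where the primary test and hypotheses 1 to 7 have already rejected.

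A reporting point is linked to this. The non-stratified difference sits close to today's strata-adjusted p-value, but it would sit less close to a baseline-adjusted one. If the test changes, the reported difference should change with it.

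**Working it through.** **Plan's own figure.** SAP 1.3 sizes the trial on mTSS: difference 0.62, SD 2.7, 90% power, two-sided 0.05. n per arm = 2 × (1.960 + 1.282)² × 2.7² / 0.62² = 399, against the stated 400. This reproduces. The documents state no rate, effect or power for DAS28(CRP)<2.6.

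**Steps ahead of hypothesis 8.** Hypotheses 4 and 5 are the mTSS tests. Assume the 0.62 effect holds for 100 mg + MTX as well.
- 400 vs 400: SE = 2.7 × √(2/400) = 0.191, power 90.1%.
- 200 vs 400: SE = 2.7 × √(1/200 + 1/400) = 0.234, power 75.5%.
- The shared control gives correlation (1/400) / √[(2/400)(1/200 + 1/400)] = 0.408, and joint power 70.7%.

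**Power for DAS28(CRP)<2.6.** Every DAS28 input here is assumed. Four-arm simulation, 400/200/200/400, 12,000 runs per setting (Monte Carlo SE about 0.4 points on a power of 70%). It uses five regions by serostatus, 10% missing outcomes counted as non-responders (rates are after NRI), and 2% missing baselines set to the mean. The correlation is that of baseline with a latent Week 24 score. Entries are power (%), strata only → plus baseline.

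| Comparison | Corr. 0 | Corr. 0.3 | Corr. 0.5 |
|---|---|---|---|
| 30% vs 40%, 400 vs 400 | 85.9 → 85.8 | 85.5 → 86.9 | 85.3 → 89.9 |
| 30% vs 40%, 200 vs 400, first arm | 70.0 → 70.0 | 70.3 → 72.6 | 69.6 → 75.6 |
| 30% vs 40%, 200 vs 400, second arm | 69.8 → 69.9 | 70.1 → 71.6 | 69.8 → 75.0 |
| 30% vs 46%, 400 vs 400 | 99.7 → 99.7 | 99.8 → 99.9 | 99.8 → 99.9 |
| 30% vs 46%, 200 vs 400 | 97.6 → 97.5 | 97.3 → 98.0 | 97.3 → 98.5 |

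A simpler simulation without strata (2,500 runs, error about 1 point or less) at 30% vs 40% and correlation 0.5 gives 84.7 → 90.0 (400 vs 400) and 67.7 → 75.3 (200 vs 400). At 0.3 it gives 84.8 → 87.2 and 66.3 → 69.8, and at 0 it shows no gain.

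**Validity.** In the four-arm simulation, type I error is 4.4–5.2% strata only and 4.5–5.6% with baseline. When baseline is prognostic only below its mean, so that linearity fails, type I error stays at 4.5–5.2%. The gain at 30% vs 40% then falls to 1.1–1.6 points (0.3) and 3.7–4.5 points (0.5).

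**Effect further down the hierarchy.** Chance that hypotheses 8, 9 and 10 all reject, at correlations 0 / 0.3 / 0.5:
- 30% vs 40%: 50.0 → 50.0, 49.8 → 52.6, 49.2 → 57.5%. Gain × 0.707: 0, 2.0 and 5.8 points.
- 30% vs 46%: 95.2 → 95.2, 94.9 → 96.1, 94.8 → 97.0%. Gain × 0.707: 0, 0.9 and 1.6 points.

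These products treat mTSS and DAS28 as independent and let every other step pass.

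**Test against interval.** Share of trials in which the p-value and the 95% CI disagree on significance, 200 vs 400, 30% vs 40%:
- as planned: 2.2–2.6%;
- baseline added, non-stratified CI kept: 7.1–7.4% (0.3) and 11.6–11.9% (0.5);
- baseline added, difference standardised from the same model: 0.5–0.7%.

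In the simpler simulation the unadjusted and standardised differences both average about 0.10 when the true difference is 0.10, so neither is biased.

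**The case against.** The strongest reply is that nothing here is an error. DAS28(CRP)<2.6 is the only binary endpoint of the five, and the SAP treats binary endpoints uniformly: one logistic model with treatment and strata, explained in 6.5. Comparing it with four continuous endpoints in an MMRM mixes outcome types. The gain rests on rates and a correlation that no document gives, and it may be nil. Changing only the DAS28 endpoints also leaves HAQ-DI reduction ≥0.22 on strata only, although a subject starting below 0.22 cannot reach it.

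Most of this stands as a description. The planned specification is coherent and the gain is conditional. It does not show a drawback to adjusting for a score that the SAP already derives. The HAQ-DI responder endpoint is fairly raised, but it is an other secondary endpoint with nominal p-values, outside the hierarchy; a sentence in 3.3 saying which endpoints carry baseline would settle it.

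Three stronger readings are tempting and unsupported:
- A reader might infer that the strata-only test is invalid. Its type I error is near 5%, and it follows the protocol.
- A reader might infer that SAP 3.3 contradicts 6.3.2, since 3.3 speaks of baseline values as covariates. It defers to Section 6 for the specification, so this is loose wording rather than a conflict.
- A reader might infer that the non-stratified difference is wrong. It is unbiased; the case for replacing it is agreement with the test.

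**Conclusion.** This is an optional improvement and not a flaw. The planned test of DAS28(CRP)<2.6 is valid. It leaves precision unused to the extent that baseline DAS28(CRP) is prognostic, which the documents do not let anyone quantify.

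Under assumed rates of 30% vs 40% the gain is about 0, 1–2 and 5–7 power points at correlations 0, 0.3 and 0.5. At 30% vs 46% it is about 1 point or less. The carry-forward to hypothesis 11 is smaller and also depends on an equal mTSS effect at 100 mg; it is a conditional figure and not a general bound. At correlation 0 adjustment costs nothing measurable. If the test is adjusted, the reported difference should come from the same model, for coherence.

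**What to change.** Before the Week 24 unblinding:

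1. **6.3.2, test.** Use logistic regression on treatment, geographic region, RF/anti-CCP status and continuous baseline DAS28(CRP). Set a missing baseline to the overall mean, so that NRI still counts every FAS subject.
2. **6.3.2, estimate.** Report the response-rate difference standardised over the FAS from that model, with a delta-method 95% CI. This suits the sparse strata noted in 6.5 better than stratum weighting. The non-stratified difference may stay as descriptive.
3. **6.3.3.2, MI.** The text classifies imputed scores against a cut-off of 3.2 or lower at Week 12; correct this to <2.6 at Week 24. It also admits only subjects with a measured baseline; apply the same missing-baseline rule so that MI and the main test cover the same subjects. The OC and LOCF analyses follow automatically: "The analysis using the same logistic regression model specified in Section 6.3.2 will be performed by using OC and LOCF methods".
4. **Appendix 6.** Add baseline DAS28(CRP), with the same fill, as a continuous variable in the DAS28 imputation model. Reconcile its three strata variables with the two stratification factors in 3.3.
5. **6.4.2, 3.3 and 6.5.** Use the same model for DAS28(CRP)<2.6 and ≤3.2 at the other visits, state in 3.3 which endpoints carry a baseline covariate, and list the change in 6.5.

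The ACR20 model in 6.2.3 needs no change. The cost is edits to these sections and some code, one more documented departure from the protocol's strata-only adjustment, a linearity assumption, and a simple fill for missing baselines.

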On-treatment assessments will include: adverse events (AEs), concomitant medications, review of study medication compliance through drug accountability, SJC66, TJC68, Subject's Global Assessment, Subject's Pain Assessment, HAQ-DI, Functional Assessment of Chronic Illness Therapy-Fatigue (FACIT-Fatigue), Short-Form Health Survey (SF-36), Work Productivity and Activity Impairment- Rheumatoid Arthritis (WPAI-RA), EuroQol 5 Dimensions (EQ-5D), CCI [REDACTED] Treatment Satisfaction Questionnaire for Medication (TSQM), Healthcare Resource Utilization, Physician's Global Assessment, physical examination, weight, vital signs, serum CRP, blood and urine sampling for safety laboratory tests and biomarkers at selected visits, and urine pregnancy tests (females of child bearing potential only).

A resting 12-lead ECG should be performed at Screening, Weeks 12, 24, 36, and 52 or ET, and at the Post-treatment Week 4 follow-up visit. ECGs should be interpreted by the investigator (or qualified designee) for clinical significance.

For all subjects, blood samples for PK analysis should be collected at least 30 minutes post study drug dose on Week 4, prior to study drug administration on Weeks 12 and 24, and any time at the final assessment visit on Week 52 or ET.

CCI [REDACTED]

Blood samples for biomarker analysis should be collected at Day 1, Weeks 4, 8, 12, 24, 36, and Week 52 or ET and urine samples should be collected at Day 1, Weeks 12, 24, and Week 52 or ET.

Radiographs of the bilateral hands, wrists, and feet should be taken at Screening, Week 24, and Week 52 or ET. However, if a subject prematurely discontinues study participation and has had X-rays performed within the previous 12 weeks, then X-rays do not need to be repeated at the ET visit. Radiographs performed after enrollment may be done +/-7 days of the scheduled visit.

Post treatment follow-up assessments include AEs, concomitant medications, physical examination, 12-lead ECG, weight, vital signs, blood and urine sampling for safety laboratory tests, and urine pregnancy tests (females of child bearing potential only).

CCI

[REDACTED]

Test Product, Dose, and Mode of Administration:	200 mg filgotinib orally q.d. plus MTX weekly up to 20 mg 100 mg filgotinib orally q.d. plus MTX weekly up to 20 mg 200 mg filgotinib orally q.d.
--	---

Reference Therapy, Dose, and Mode of Administration:	MTX weekly up to 20 mg or PTM MTX weekly PTM filgotinib 200 mg orally q.d. PTM filgotinib 100 mg orally q.d.
---	--

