6.7. Study Assessments

6.7.1. Efficacy

Efficacy assessments will be carried out at Day 1 and at Weeks 2, 4, 8, 12, 16, 20, 24, 30, 36, 44, and 52, or at ET (if applicable).

Assessments of RA will include the derived ACR (ACR20, 50, 70 as well as ACR-N and EULAR response criteria, DAS28 [CRP], CDAI, and SDAI as well as the individual components of the ACR response criteria [TJC68, SJC66], HAQ-DI, Physician's Global assessment, Subject's Global Assessment, Subject's Assessment of Arthritis Pain and CRP]) and radiographs of hands, wrists and feet (mTSS and mTSS components of erosion score and joint space narrowing).

Additionally, subjects will be asked to complete questionnaires, including the FACIT-Fatigue scale, SF-36, EQ-5D, TSQM, WPAI-RA at Day 1 and at Weeks 4, 12, 24, 36, and 52, or at ET (if applicable). Healthcare resource utilization will be assessed at the Day 1 and at Weeks 12, 24, 36 and 52, or at ET (if applicable).

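### The Week 24 MMRMs let the treatment effect, but not the baseline slope, vary by visit; this can cost a little precision, mainly for HAQ-DI

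*SAP*

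**What the plan says.** SAP 6.3.2 analyses the Week 24 HAQ-DI change with a "mixed-effects model for repeated measures (MMRM) that include all available data at postbaseline visits". The model is fitted "with baseline value, stratification factors, treatment, visit, and treatment by visit interaction included as fixed effects and subject being the random effect", and "An unstructured variance-covariance matrix will be used". The other continuous key secondary endpoints (SF-36 PCS, FACIT-Fatigue and mTSS) "will be analyzed using similar MMRM method as HAQ-DI, by including all available data at postbaseline visits".

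SAP 6.4.2 repeats the structure: "The MMRM models will include baseline value, stratification factors, treatment, visit, and treatment by visit interaction included as fixed effects". The subgroup models in SAP 6.3.4 and the MMRM in Protocol 8.5.2 also carry a single baseline term.

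The visits that share this one slope differ by endpoint:
- **HAQ-DI:** 11 postbaseline visits. Protocol 6.7.1 states: "Efficacy assessments will be carried out at Day 1 and at Weeks 2, 4, 8, 12, 16, 20, 24, 30, 36, 44, and 52".
- **SF-36 PCS and FACIT-Fatigue:** 5 postbaseline visits, the first at Week 4. The same section lists questionnaires "including the FACIT-Fatigue scale, SF-36, EQ-5D, TSQM, WPAI-RA at Day 1 and at Weeks 4, 12, 24, 36, and 52".
- **mTSS:** 2 postbaseline visits. The protocol synopsis states: "Radiographs of the bilateral hands, wrists, and feet should be taken at Screening, Week 24, and Week 52 or ET".

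The multiple imputation and tipping-point analyses in SAP 6.3.3.2 reuse the 6.3.2 model for the continuous endpoints. No single-visit ANCOVA is planned beside it.

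**The concern.** A treatment-by-visit term with no baseline-by-visit term frees the treatment effect over time but holds the regression on baseline fixed. For a score such as HAQ-DI, the correlation between baseline and a later visit usually falls as time passes, so the slope of change on baseline becomes more negative. A slope pooled over Weeks 2 to 52 is then drawn toward the early visits and under-adjusts the Week 24 change. The unstructured covariance does not cure this, because the restriction lies in the mean model.

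HAQ-DI at Week 24 is hypotheses 2, 3 and 7 in the fixed sequence of SAP 3.5. Failing 2 or 3 ends formal testing before the mTSS hypotheses (4 and 5), and mTSS is the endpoint on which the trial was sized. Hypotheses 3 and 7 also use the 200-subject arms. Any precision lost here could be recovered from data already collected.

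**Working it through.** **1. The plan's own figure.** SAP 1.3 gives a difference of 0.62, SD 2.7, two-sided 0.05 and 90% power for mTSS. n per arm = 2 × (1.960 + 1.282)² × 2.7² / 0.62² ≈ 399, and 400 per arm gives 90.1%. The stated figure reproduces. It is a plain two-sample calculation and takes no credit for baseline adjustment.

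**2. Formula.** Let β be the vector of true visit-specific slopes of change on baseline, and S the covariance of the visits given baseline. With unstructured covariance and a full treatment-by-visit term, the common slope converges to

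b = 1′S⁻¹β / 1′S⁻¹1.

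Relative to a model with baseline-by-visit, the variance of the Week 24 contrast is multiplied by

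VIF = 1 + (β₂₄ − b)² × Var(baseline) / S₂₄.

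If the correlation with baseline does not change over time (and the SD is stable), all slopes are equal, b = β₂₄ and VIF = 1.

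**3. One HAQ-DI scenario (assumed).** Take equal SDs, scaled to 1, and a Week 24 correlation with baseline of 0.35. Then β₂₄ = 0.35 − 1 = −0.65 and S₂₄ = 1 − 0.35² = 0.8775. The common slope was −0.43. VIF = 1 + 0.22² / 0.8775 ≈ 1.055 (1.056 unrounded). A 3000-run simulation with 400 per arm gave:
- variance ratio 1.07;
- power 87.9% with the common slope, 89.6% with baseline-by-visit;
- type I error 5.1% against 4.4% (Monte Carlo SE about 0.4 points);
- bias about 0.001 for both.

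**4. Range of assumptions.** The documents give no HAQ-DI SD, baseline correlation or visit slope. For the questionnaire endpoints, 750 scenarios with complete data were evaluated. They varied the stable share of correlation (0.1-0.5), visit noise (0.05-0.3), decay constant (4-104 weeks) and SD relative to baseline (0.8-1.25). If the by-visit model has 90% power, the common-slope model has Φ(3.242/√VIF − 1.960). For VIF 1.077 this is Φ(3.124 − 1.960) = 87.8%.

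| Endpoint, visits in model | VIF median | 90th percentile | Maximum | Power at each |
|---|---|---|---|---|
| HAQ-DI, all 11 | 1.020 | 1.077 | 1.17 | 89.4 / 87.8 / 85.0% |
| HAQ-DI, to Week 24 only (7) | 1.035 | 1.121 | 1.27 | 89.0 / 86.5 / 82.1% |
| SF-36 PCS, FACIT-Fatigue, all 5 | 1.009 | 1.037 | 1.09 | 89.7 / 88.9 / 87.5% |
| SF-36 PCS, FACIT-Fatigue, to Week 24 only (3) | 1.021 | 1.072 | 1.16 | 89.4 / 87.9 / 85.4% |

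Week 24 was under-adjusted in 97% or more of these scenarios. At the Week 24 analysis (SAP 2.2) later visits are only partly observed, so the applicable figure lies between the paired rows. The maxima are corner cases.

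**5. mTSS.** With assumed baseline SD 5-30 and Week 24 slope 0-0.05, the median VIF was 1.000 and the 90th percentile 1.009. The common slope over-adjusted in 37% of scenarios and under-adjusted in 23%. One extreme corner reached 1.71, by over-adjustment.

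**6. What this means for the HAQ-DI tests.** Assume SD 0.63 and correlation 0.5, so the residual SD is 0.63 × √0.75 = 0.546. For 200 against 400 the SE is 0.546 × √(1/200 + 1/400) = 0.047. Raising the variance by 7% changes power as follows:

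| Assumed difference | 400 vs 400 | 200 vs 400 |
|---|---|---|
| 0.20 | 99.9 → 99.9% | 98.8 → 98.3% |
| 0.15 | 97.3 → 96.4% | 88.7 → 86.6% |
| 0.10 | 73.6 → 70.7% | 56.2 → 53.4% |

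**The case against.** The strongest reply is that this is a preference about efficiency. The model is prespecified and valid, Protocol 8.5.2 already used a single baseline term, and the typical HAQ-DI loss is about 2% of variance with all visits. The larger figures need either little data after Week 24 or a correlation that decays steeply with almost no visit-level noise. Under pure exponential decay, for example, a Week 24 correlation of 0.5 implies a Week 2 correlation of 0.5^(2/24) = 0.94, which is high for a questionnaire. If HAQ-DI power is already high, the change is under one point. All of this stands, and it limits the size of the point. It does not remove it, because the term is absent and adding it is nearly free.

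A reader might also infer that every Week 24 MMRM is under-adjusted by a slope pooled from Week 2 onward. The documents do not support that. Only HAQ-DI has visits from Week 2; SF-36 PCS and FACIT-Fatigue start at Week 4. mTSS has no visit before Week 24 to pull the slope, so the mechanism does not carry over to it.

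**Conclusion.** The point holds as a modest loss of efficiency that can be avoided. If the correlation with baseline falls over time, the pooled slope under-adjusts the Week 24 HAQ-DI change. Typical variance inflation is about 2-4%, with a range of 0 to about 8% with all visits and up to about 12% if little data exist after Week 24. At the typical values this is like losing about 8 to 14 of 400 subjects per arm (400 − 400/1.02 = 8; 400 − 400/1.035 = 14). Power falls by roughly 0-3 points, and by 3.5 at the 12% figure if power was 90%. For SF-36 PCS and FACIT-Fatigue the inflation is typically about 1-2%, and up to about 4% with all visits. For mTSS it is about 0, and its direction is uncertain.

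Every size rests on assumed correlations; only the absence of the term is certain from the documents. Two stronger conclusions would be wrong. First, the Week 24 tests are not biased or anti-conservative: with complete randomized data the contrast is essentially unbiased and type I error is held. If missing Week 24 values depend on baseline, a wrong slope could add a small bias, which was not quantified. Second, the trial does not miss its stated power, because the 90% for mTSS assumes no gain from baseline adjustment.

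**What to change.** Before unblinding for the Week 24 analysis:
- In SAP 6.3.2, add the baseline-by-visit interaction to the fixed effects of the HAQ-DI model. The SF-36 PCS, FACIT-Fatigue and mTSS models, and the sensitivity analyses that reuse them, then follow.
- Use the same specification for the subgroup MMRMs in 6.3.4 and the other continuous endpoints in 6.4.2, so that main and supporting models agree.
- List the change in 6.5, since Protocol 8.5.2 names a single baseline term.

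The cost is a short text change in four sections and one extra parameter per visit after the first: 10 for HAQ-DI, 4 for SF-36 PCS and FACIT-Fatigue, and 1 for mTSS, with about 1200 subjects. No new data are needed, and there is no type I error cost if it is settled before unblinding.
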